### 4.5 EXPLORATORY EFFICACY ENDPOINTS

Additional endpoints of interest include:

- Index procedure resource utilization: Anesthesia, procedure time and time to discharge.
- Follow up resource utilization: Nasal airway obstruction related return visits and medication utilization.
- Subject satisfaction questionnaire at 1, 3 and 12 months.
- Degree of nasal way obstruction as reported by subjects on the VAS scale at baseline with decongestant use.
- Endoscopic lateral wall insufficiency score per side21 at baseline and 6 months

- 3-D camera lateral wall motion assessment per side at baseline and 3, 6 and 12 months (at select sites).
- Cosmesis changes from baseline evaluated by Independent Photo Review 3 and 6 months (at select sites).
- Allergic rhinitis status at 1, 3, 6 and 12 months.
- Nasal geometry: length of nose, height and width of nose, skin thickness of lateral wall at baseline.
- Type of turbinate procedure.

### 4.6. MULTIPLICITY ADJUSTMENT

All type-1 error will be allocated to the primary hypothesis, and there will be no adjustments for multiple testing.

### SAFETY

All safety analyses and summaries will be based on the ITT and mITT analysis.

#### 5.1. ADVERSE EVENTS

Adverse events (AEs) will be coded. Adverse events through 7 days post procedure will be summarized for the ITT analysis set, and cumulative summaries will be produced for the mITT analysis set.

Categories of adverse events include:

- Device-related AEs
- Implant procedure-related AEs
- Serious AEs
- Adverse Device Effect (ADE)
- Device retrievals
- Moderate or Severe AEs

Summaries may also be produced by follow-up interval.

For each AE category, the percentage of subjects who experienced at least one occurrence of the given event will be calculated. Overall frequency by coded type will also be summarized. In addition, each AE will be listed for each subject. These listings will include onset interval, relationship to procedure and implant, severity, whether the event is an ADE, SADE or SAE, onset and resolution dates, action taken and outcome.

If the timing of events such as implant retrieval is of interest, this will be analyzed using Kaplan-Meier techniques.

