4.2. STUDY ENDPOINTS

4.2.1. PRIMARY ENDPOINTS

Primary Efficacy Endpoint: Proportion of treatment responders at 6 months post procedure.

• Responder is defined as subject that has at least 1 NOSE class improvement or at least 20% NOSE score reduction

Primary Safety Endpoint: Nasal procedure and Latera device-related adverse events through 6 months.

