8. ASSESSMENT OF SAFETY

8.1. SPECIFICATION OF SAFETY PARAMETERS

All Serious Adverse Events (SAE), Adverse Device Effect (ADE) and Serious Adverse Device Effects (SADE) will be collected and documented through the end of subject participation in the study. In addition, all non-serious device and procedure-related Adverse Events (AE) and all non-serious head and neck, and/or respiratory related AEs will also be collected and documented.

The primary safety endpoint evaluation will consider nasal procedure related and Latera related adverse events through 6 months post-procedure.

The following information for each AE, ADE, SAE and SADE will be collected:

- Date of onset
- Status and/or Outcome
- Date of resolution
- Adverse Event/Effect type
- SAE or SADE
- Severity of event
- Relation to Study Device and/or procedure
- Action taken
- Descriptive narration of Event/Effect

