10.4.4. SAFETY ANALYSES

Two analysis sets will be used to *summarize* adverse events. The ITT analysis set will be used to summarize acute adverse events (through 1 month post procedure), and the mITT analysis set will be used to summarize adverse events over the entire duration of follow-up. The primary safety reporting time-point is 6 months post-implant.

The overall incidence (i.e., number and percent of subjects with 1 or more adverse event in each class) of adverse events, serious adverse device events, serious adverse events, fatal adverse events, and device related events (e.g., possibly, probably or definitely related) will be calculated for the acute phase, through 6 months post-procedure and for the entire duration of follow-up. The overall incidence of mild, moderate and severe events will be calculated by considering the most severe event for each subject.

In addition, the overall incidence for each adverse event type will be calculated. The adverse event types will be classified according to the following categories:

- Excessive Inflammation
- Significant Foreign body sensation
- Excessive Pain or discomfort
- Infection
- Implant Extrusion, defined as body rejection of implants
- Implant Retrievals, defined as surgeon or subject initiated removal of implants not associated with body rejection of implant
- Implant bent or fractured
- Implant loose
- Implant migration
- Skin irritation
- Hematoma
- Unintended perforation of the skin
- Other

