# 2.2.1. ANALYSIS SETS FOR EFFICACY AND SAFETY

The ITT analysis set will primarily be used for safety evaluations and will include all subjects who begin the implant procedure. Subjects who are consented but do not begin the implant procedure will not be included in the ITT analysis set. Because this is a singlearm, open-label study, the exclusion of subjects who do not begin the implant procedure is unlikely to result in biased response estimates. Subjects who begin the implant procedure but do not successfully receive an implant will be included in the ITT analysis set.

The mITT analysis set will consist of all subjects who successfully receive at least 1 Spirox LateraTM implant. Analyses supporting the primary and major secondary endpoints will, to the extent possible, be based on the mITT analysis set. Safety evaluations for events within 7 days of the implant procedure will be based on the ITT analysis set, and cumulative adverse events at 6 months will be based on the mITT analysis set. An important subgroup of the mITT analysis set is the 6 Month Evaluable (6ME) Set, which includes subjects with 6 month post-implant NOSE score assessments in clinic or by telephone.

The per-protocol (PP) analysis set will consist of all mITT subjects who have no major protocol deviations or events that might impact NOSE scores. These deviations may include changes to background nasal medications, prohibited medications and additional procedures prohibited by the protocol.

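### The SAP shortens the ITT adverse-event summary from 1 month to 7 days without explanation and, with 6-month safety on mITT, later events in subjects who received no implant reach only the listings

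*SAP*

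**What the plan says.** Protocol 4.2.1 defines the "Primary Safety Endpoint: Nasal procedure and Latera device-related adverse events through 6 months". Protocol 8.1 repeats it: "The primary safety endpoint evaluation will consider nasal procedure related and Latera related adverse events through 6 months post-procedure".

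Protocol 10.4.4 names two sets for adverse events. ITT (everyone in whom the implant procedure began) is for "acute adverse events (through 1 month post procedure"). For the rest, "the mITT analysis set will be used to summarize adverse events over the entire duration of follow-up". The same section adds: "The primary safety reporting time-point is 6 months post-implant". As ITT is assigned only to the first month, the protocol's 6-month summary falls to mITT.

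SAP 5.1 changes the first of these: "Adverse events through 7 days post procedure will be summarized for the ITT analysis set", with the cumulative summaries on mITT. SAP 2.2.1 gives the same 7-day limit and states that "cumulative adverse events at 6 months will be based on the mITT analysis set". It also says that subjects who begin the procedure without successfully receiving an implant belong to ITT; mITT requires at least one successful implant. Neither SAP section explains the move from 1 month to 7 days.

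**The concern.** Subjects in whom the procedure began but no implant was placed sit in ITT and not in mITT. The analysis set assigned to each time window therefore decides whether their events are counted in any rate.

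These subjects are exposed to part of what the primary safety endpoint measures. Under Protocol 7.1.3, planned septoplasty or turbinate reduction comes first and implant delivery is the last step, so a subject whose delivery fails may already have had the concurrent surgery. Protocol 8.2.2 assesses relatedness to those concomitant procedures as its own category. Protocol Appendix II reports concurrent procedures in 89% of commercial cases. Protocol 2.3.2 lists hematoma from cannula insertion and skin perforation among the implant-procedure risks, and an attempt alone can cause either.

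At stake is whether the 6-month safety rate describes everyone who underwent the procedure or only those in whom placement succeeded. SAP 2.2.1 argues that leaving out subjects who never begin the procedure is unlikely to bias the response estimates. It offers no argument for leaving failed attempts out of 6-month safety.

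**Working it through.** The documents state no figure to reproduce. The check has three steps: compare the texts, confirm that no other provision closes the gap, and bound the possible effect.

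**1. Where an event is counted when no implant was placed**

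| Onset of event | Protocol 10.4.4 | SAP 2.2.1 and 5.1 |
|---|---|---|
| Through day 7 | ITT acute rate | ITT 7-day rate |
| Day 8 to 1 month | ITT acute rate | no specified rate |
| After 1 month, through 6 months | no specified rate | no specified rate |

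The SAP's own change is the middle row. Taking a month as 30 days, that is 30 − 7 = 23 days. The last row is common to both documents.

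**2. Other provisions**

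- The opening sentence of the SAP's safety section says safety uses ITT and mITT. It names no window, so it does not extend the 7 days fixed in 2.2.1 and 5.1.
- The optional summaries by follow-up interval in SAP 5.1 name no set. SAP 2.2 makes mITT the default.
- SAP 3.4.1 tabulates adverse events during the procedure in ITT. That covers the procedure itself, not later onset.
- SAP 5.1 lists every adverse event by subject. A listing reports the event but has no denominator.

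**3. Possible size**

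Notation:

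- N = 170, the maximum enrolment (Protocol 5.3), assuming all begin the procedure.
- f = subjects with no implant placed. Not given; 1 to 9 assumed.
- p = 6-month related-event rate in mITT. Not given; about 10% assumed, rounded to whole subjects.
- q = proportion of the f subjects with a related event that the mITT rate omits. Not given; taken from 0 to 1.

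ITT rate = [(N − f)p + fq] / N, so ITT rate − mITT rate = (f/N)(q − p).

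| f | mITT rate | ITT rate, q = 0 | ITT rate, q = 1 |
|---|---|---|---|
| 1 | 17/169 = 10.1% | 17/170 = 10.0% | 18/170 = 10.6% |
| 3 | 17/167 = 10.2% | 17/170 = 10.0% | 20/170 = 11.8% |
| 5 | 16/165 = 9.7% | 16/170 = 9.4% | 21/170 = 12.4% |
| 9 | 16/161 = 9.9% | 16/170 = 9.4% | 25/170 = 14.7% |

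Intermediate cases with p at exactly 10%:

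- f = 2, one subject with an event: (16.8 + 1)/170 = 10.5%. Relative to the ITT rate, mITT understates by (10.47 − 10)/10.47 = 4.5%.
- f = 9, four subjects with events: (16.1 + 4)/170 = 11.8%. The understatement is (11.8 − 10)/11.8, about 15%.

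The sign depends on whether q exceeds p, and the documents do not settle that.

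**The case against.** The case against giving this much weight is substantial, and most of it stands as a limit on the point.

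- A reader might infer that safety follow-up is cut. It is not. Only a summary window changes: Protocol 7.1.4 and 8.1 leave collection intact, and late events are still listed.
- A reader might infer that the SAP moved 6-month safety to mITT. It did not. Protocol 10.4.4 already uses mITT for the whole of follow-up.
- A reader might infer that mITT drops everyone in whom the procedure went wrong. It needs only one successful implant, so a bilateral case failing on one side stays in. So does a subject with a skin perforation or device malfunction who has an implant placed. Appendix II reports about 90% bilateral placement in commercial use, so complete failure would usually mean failure on both sides.
- A reader might infer a downward-biased rate. That holds only if q exceeds p. With 5 failures and no late events, the ITT rate is 9.4% against 9.7% in mITT.
- A 7-day cut that matches no visit is not a defect, because onset dates are recorded (Protocol 8.1).
- Extrusion, migration, loosening, fracture and retrieval can occur only with an implant in place. For these mITT is the at-risk denominator, and ITT would dilute the rate.
- The safety endpoint is descriptive; Protocol 10.2 sets a formal hypothesis for efficacy only.

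None of this reconciles the two ITT windows or supplies a 6-month rate for procedure-related events among all subjects who underwent the procedure.

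**Conclusion.** The point holds as an unexplained conflict between protocol and SAP on the ITT window, together with a gap common to both documents at the primary safety time point. It rests on the text alone. It reads the endpoint's nasal procedure as covering the implant attempt and any concurrent surgery, as the two relationship categories in Protocol 8.2.2 suggest.

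The effect on the reported rate cannot be determined. Under the assumptions above, with 5 failed attempts among 170, the ITT rate differs from mITT by between −0.3 points (9.4 − 9.7) and +2.7 points (12.4 − 9.7). The upper end needs an omitted event in every failed attempt. The effect is probably small if complete failures are rare, and neither document gives their number. The documents do not support calling the rate biased. They do show that it is conditional on successful placement, while the endpoint is not defined that way.

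**What to change.** 1. In SAP 2.2.1 and 5.1, restore the protocol's 1-month window for the ITT summary of acute events.
2. In SAP 2.2.1 and 5.1 and Protocol 10.4.4, report the 6-month primary safety endpoint (nasal procedure- and device-related events) for ITT alongside mITT.
3. Keep mITT as the denominator for extrusion, migration, loosening, fracture and retrieval.
4. With the ITT table, state how many subjects received no implant and how many of them were followed to 6 months. Neither document says how they are followed, and the SAP 3.3 disposition line for discontinuation before 6 months covers mITT only. If they exit early, the ITT rate is itself incomplete.

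The cost is wording in both documents and one extra table. Protocol 8.1 already requires related events to be collected through the end of participation, so no new data item is needed. The downside is that the added rate may be slightly less favourable.

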To date, all follow up visits through 18 months have been completed; 15 out of 30 subjects completed 18 months of follow up. Three subjects have had other nasal surgery procedures and consequently exited the study; two subjects after the 12 month visit and one subject after the 18 month visit.

		Score	Change from baseline			Change from baseline % Change from baseline			Change from baseline	
Visit	N	Mean (SD)	Mean (SD)	LS Mean (95% CI)	p-value	Mean (SD)	LS Mean (95% Cl)	p- value		
1 Week	30	24.2 (16.14)	-52.5 (22.77)	-52.7 (-58.83, -46.55)	<.001	-67.2 (21.34)	-67.2 (-74.98, -59.51)	<.001		
1 Month	30	27.0 (23.95)	-49.7 (25.56)	-49.9 (-58.79, -40.93)	<.001	-64.8 (29.09)	-64.9 (-75.92, -53.86)	<.001		
3 Months	29	28.4 (26.90)	-48.4 (27.84)	-47.9 (-57.85, -37.96)	<.001	-63.4 (34.45)	-62.7 (-75.70, -49.66)	<.001		
6 Months	30	33.3 (29.69)	-43.3 (31.28)	-43.5 (-54.61, -32.44)	<.001	-56.2 (37.85)	-56.3 (-70.46, -42.07)	<.001		
12 Months	29	35.2 (29.17)	-40.9 (31.23)	-39.7 (-51.22, -28.11)	<.001	-53.1 (40.64)	-51.6 (-67.07, -36.12)	<.001		
18 Months	15	38.0 (33.32)	-41.7 (36.24)	-40.7 (-55.01, -26.30)	<.001	-51.3 (41.76)	-52.2 (-70.59, -33.87)	<.001		

A longitudinal summary of NOSE score is provided in the table below and these results demonstrate significant improvements over baseline for all time points measured.

This first in man study demonstrated the safety and effectiveness of the absorbable Implant to provide lateral cartilage support in patients with NVC as primary contributor to NAO.

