#### MAJOR SECONDARY ENDPOINTS 4.4.

#### 4.4.1. DEFINITIONS

The secondary efficacy endpoints are:

- Proportion of treatment responders at 1, 3, 12, 18 and 24 months post procedure.
- Change in nasal airway obstruction from baseline to 1,3, 6, 12, 18 and 24 months as reported by subjects on the VAS scale.
- Subject satisfaction questionnaire at 6 months.
- Procedure and device-related adverse events though 24 months.

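### The 24-month adverse-event rate is a crude percentage of implanted subjects and Kaplan-Meier is optional, so loss after month 12 biases late device-effect rates downward

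*SAP*

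**What the plan says.** SAP 5.1 defines the adverse-event measure: "For each AE category, the percentage of subjects who experienced at least one occurrence of the given event will be calculated". For the period beyond the first 7 days, "cumulative summaries will be produced for the mITT analysis set". SAP 2.2.1 defines that set without reference to length of follow-up: "The mITT analysis set will consist of all subjects who successfully receive at least 1 Spirox" implant.

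Protocol 10.4.4 agrees. Incidence is the "number and percent of subjects with 1 or more adverse event in each class", and "the mITT analysis set will be used to summarize adverse events over the entire duration of follow-up". Neither document gives an at-risk denominator or says how an early leaver enters the percentage.

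The SAP does have a way to handle censoring. SAP 3.5 defines follow-up for time-dependent safety analyses as running to the first event or to the last date on which the event could be assessed. SAP 5.1, however, makes its use conditional: "If the timing of events such as implant retrieval is of interest, this will be analyzed using Kaplan-Meier techniques". Summaries by follow-up interval are also optional. Neither is tied to the 24-month secondary endpoint in SAP 4.4.1, "Procedure and device-related adverse events though 24 months".

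On follow-up itself, subjects agree at entry to 12 months (Protocol 5.1, criterion 7), and the schedule in Protocol 7.7 calls for re-consent at month 12 for the 18- and 24-month contacts. Protocol 7.1.4 and 7.7 limit collection after month 12 to adverse device effects.

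**The concern.** A percentage of a fixed set of implanted subjects treats unobserved time as time without an event. If loss is unrelated to events, the error runs one way, towards a lower rate, and so in the device's favour. It grows with the share of subjects not seen in the second year. Here that share depends on a fresh consent at month 12, and the implant is described as absorbing over about 18 months, inside the re-consented period. Late device effects are thus the events for which the denominator is least secure.

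Precision is affected in the same way. SAP 5.1 names no confidence interval for any safety rate, and one computed on all implanted subjects would look tighter than the observed follow-up supports.

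**Working it through.** **The plan's own figures on loss.** The documents state no adverse-event rate, so the nearest figures to reproduce are those for enrolment and dropout.

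- SAP 1.4: 120 evaluable at 6 months with 20% dropout gives 120 / 0.80 = 150, as stated.
- Protocol 10.5: 150 with about 10% dropout gives 150 / 0.90 = 166.7, so 167, consistent with up to 170.
- Protocol 5.3: 170 enrolled to have 150 complete 24 months. Planned loss is 20 / 170 = 11.8%.

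**Inputs for the check.**

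- True 24-month incidence of a first device effect, p = 5%. This is an assumption.
- Loss q: 11.8% (Protocol 5.3), 20% (the SAP 1.4 dropout figure, used there for 6 months), 30% (assumed), and 50% (Protocol 2.2: "15 out of 30 subjects completed 18 months of follow up").
- Loss unrelated to events.

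**Expected crude percentage under three patterns.**

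(a) All events come after all the loss: crude = p(1 − q).

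(b) Constant event hazard, all loss at month 12. Per-year risk a = 1 − √0.95 = 0.02532. Crude = a + (1 − a) × a × (1 − q) = 0.02532 + 0.02468 × (1 − q).

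(c) Constant event and loss hazards. With h = −ln(1 − p) and d = −ln(1 − q), crude = h / (h + d) × [1 − exp(−(h + d))].

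| Loss q | (a) | (b) | (c) |
|---|---|---|---|
| 11.8% | 4.41% | 4.71% | 4.70% |
| 20% | 4.00% | 4.51% | 4.49% |
| 30% | 3.50% | 4.26% | 4.21% |
| 50% | 2.50% | 3.77% | 3.62% |

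The shortfall from 5% is 0.3-0.6 points at planned loss, 0.7-1.5 points at 30% and 1.2-2.5 points at 50%. The relative shortfall hardly depends on p. Under (b) at 50% loss it is 24.9%, 24.7% and 24.3% for true rates of 2%, 5% and 10%.

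**What Kaplan-Meier returns.** Under (b), the conditional risk in year two is estimated among those still followed, so the estimate is 1 − (1 − a)² = 1 − 0.95 = 5%, whatever q is.

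**Six months.** Formula (c) depends only on p and q over the window. If 20% were lost evenly by month 6 (SAP 1.4) and the true 6-month rate were 5%, the crude figure would read 4.49%. The prior study had NOSE scores for 30 of 30 subjects at 6 months, which would make the gap negligible.

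**Precision.** With zero late events, the exact two-sided 95% upper limit is 1 − 0.025^(1/n): 2.15% for n = 170, 2.43% for n = 150 and 4.25% for n = 85 (half of 170).

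**The case against.** Crude subject incidence is a common descriptive safety summary, and neither document tests a safety hypothesis. The SAP commits to a Kaplan-Meier summary of time under follow-up (3.5), to disposition counts including 24-month completers (3.3), and to a listing of each event with its onset interval and dates (5.1). Protocol 10.4.4 reports the acute phase, 6 months and full follow-up separately. A careful reader could therefore see how many subjects were observed. This stands, but it leaves the reader to rebuild the estimate from listings.

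Several stronger readings are tempting, and the documents do not support them.

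- *Everyone who leaves is counted as event-free.* A subject with an event before leaving is still counted. Only those without a prior event are affected.
- *The denominator is stated to be all implanted subjects.* It is the natural reading of mITT, not an explicit rule.
- *Half the cohort will be missing.* The prior study still had NOSE scores for 29 of 30 at 12 months. The shortfall at 18 months is not explained, and Protocol Appendix II speaks of 18 subjects having reached that point. In this trial, months 18 and 24 can be done by telephone or mailed form, with a stipend for each.
- *Device effects cluster late.* Protocol 2.2 reports one hematoma, one inflammation and three retrievals. It attributes the retrievals to implantation technique or to manipulation in the first post-operative week. Nothing shows a rise around absorption, so pattern (a) is a limiting case.
- *The primary safety endpoint is materially biased.* Month 6 precedes re-consent, and any effect there should be small.

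Kaplan-Meier also has a limit. It assumes loss is unrelated to events, and Protocol 2.2 records three subjects who left after other nasal surgery, which may be related to outcome.

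**Conclusion.** The point holds in limited form. The only committed measure is a crude percentage on the implanted set. The method that would handle incomplete follow-up is in the SAP but optional, and it is not linked to the 24-month endpoint. Followed as written, and if loss is unrelated to events, the plan understates late device-effect rates.

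At planned retention the understatement is small. It becomes material only if many subjects do not re-consent, and the documents do not give that rate. These sizes rest on an assumed 5% rate and on assumed event timing; informative loss could change the size or direction of the bias in either estimate.

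A related inconsistency bears on the same endpoint. It covers procedure- and device-related events through 24 months (Protocol 4.2.2, SAP 4.4.1). Protocol 7.1.4 and 7.7 collect only adverse device effects after month 12, while Protocol 8.1 and 8.3 describe wider collection throughout the study. On the narrower reading, events related only to the concomitant procedure have no observed time in the second year for anyone, and no estimator can supply it.

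**What to change.** In SAP 5.1:

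1. Report Kaplan-Meier cumulative incidence with 95% CI and numbers at risk at 6, 12 and 24 months for device-related AEs and ADEs, and for implant retrieval and extrusion. Use the follow-up time in SAP 3.5 and keep the crude counts alongside.
2. For any summary by interval, use the subjects under observation in that interval as the denominator.
3. Report the number re-consenting at month 12, and compare those who did and did not re-consent.
4. Reconcile Protocol 4.2.2, 7.1.4, 7.7, 8.1 and 8.3 and SAP 4.4.1 on which events are collected after month 12. Censor at month 12 any event type not collected beyond it.

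The cost is SAP wording, one table and the reconciliation; items 1 to 3 need no new data. Late rates may look slightly less favourable, and the estimate should carry the caveat that it assumes loss unrelated to events.
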